- Pain score will be collected during the index procedure and at 7 days and 30 days.
- Return to work and return to normal activities will be assessed at follow-up visits until the subject has returned to each.
- The VenousDQoL consists of two stand-alone questions at baseline, 7 and 30 days, 6, 12, 24, 36, 48 and 60 months (data will be collected through 12 months for subjects enrolled in VenaSeal vs. Surgical Stripping Study).

Questionnaire completion by delegated site personnel

The required study questionnaires such as EQ-5D-5L, VenousTSQ, patient reported symptoms, etc. should be completed in a consistent manner throughout the study. Selecting to complete the required questionnaire on behalf of the subjects should only be if the subjects require it (e.g., vision or literacy issues) and not simply by site or patient preference. The site personnel completing the questionnaire

Medtronic Business Restricted

CONFIDENTIAL

056-F275, v B Clinical Investigation Plan Template

cannot be the treating physician or the PI in order to avoid any bias. If site personnel are assigned to complete the questionnaire on behalf of the subject for one visit, then site personnel should complete for all the remaining visits. Site personnel have to read the complete questionnaire including all the response options. Ideally, the same person will complete the questionnaire with the same subject each time, if at all possible. The questionnaires completed by site personnel may differ from subject questionnaires and may require IRB/EC approval. If necessary, due to COVID-19 restrictions, these questionnaires could also be completed and signed by the subject within 24 hours prior to the follow-up visit. If captured in this manner, care must be taken to ensure the questionnaires are completed and returned to the site prior to the completion of the rest of the visit.

Healthcare Utilization

This study will collect healthcare utilization data related to subject's VRD and care related to the VenaSeal™ closure system to demonstrate total costs over the follow-up period. Specifically, this study will collect:

- Number and type of adjunctive treatments (phlebectomy and sclerotherapy) conducted through 60 months post-index procedure.

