4. EQ-5D-5L
5. AVVQ
6. SF-36
7. Patient reported outcomes:
 - a. Pain score measured by using NRS scale of 0-10
 - b. Ability to return to work/normal activities (only if not returned to work/normal activities by 7-day visit)
 - c. VenousDQoL
 - d. Patient-reported symptoms
8. AE assessment
9. Healthcare utilization since last study visit
10. VLU Study:
 - a. Active ulcers: ulcer assessment, ongoing wound care, photographs for core laboratory, healing status
 - b. Post-healing confirmation: recurrence status.

If COVID-19 prevents patients from returning for follow-up visits at 7 or 30 days (due to subject contracting COVID-19 or due to site policy), these visits may be conducted through telehealth or other alternative methods to be discussed with the Medtronic study team prior to execution.

3+ Months (calculated as 90 days): Optional for all subjects

1. Adjunctive therapy: Number of phlebectomy sites and/or sclerotherapy injections administered (data collected through 60 months).
2. AE Assessment.

6 months (+/- 4 weeks), 12, 24, 36(+/-8 weeks)

Subjects will return to the site for follow-up to conduct the following assessments (limb-specific assessments are of the target limb only). VenaSeal vs Surgical Stripping Study subjects will be followed up to and including 12 months:

1. DUS:
 - a. Areas of patency, if any
 - b. Reflux along treatment area
 - c. Evidence of thrombus
2. CEAP classification
3. rVCSS
4. Venous Treatment Satisfaction Questionnaire (VenousTSQs) (up to 12 months visit)

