10.17.3. Lost to Follow-up

The study site will make every effort to have all subjects complete the follow-up visit schedule. A subject will not be considered lost to follow-up unless all efforts to obtain compliance are unsuccessful and the site should contact the study team before exiting the subject. At a minimum, the effort to obtain follow-up information must include three attempts to make contact via telephone and if contact via phone is not successful, a traceable letter from the investigator should be sent to the subject's last known address, a copy of which should be maintained in the subject's study record. All contact efforts to obtain follow-up must be documented in the subject's medical records.

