7.9.1.2.2 Endpoint Definition

Return to work is defined as the time in days patients need following a procedure to return to work. Employment status will be captured for all patients. Only patients who have an active employment status (employed or independent worker, including stay at home parents) will be included in the analysis for return-to-work time. Information will be captured on the category of occupation to be able to distinguish between physical and sedentary work. Patients will be censored at the time of study exit.

The other key secondary endpoint to be assessed is the primary target vein closure rate after index treatment. The primary target vein should be the saphenous vein (GSV, SSV, accessory saphenous veins) which at the investigator's discretion is most likely responsible for the greatest portion of the patient's symptoms or pathology. This vein will be treated first.

For subjects treated with the VenaSeal™ system or ETA, anatomic closure of the primary target vein is defined as Doppler ultrasound (DUS) showing primary target vein closure along the entire treated vein segment with no discrete segments of patency exceeding 5 cm. Any areas with >5 cm patency will be measured, and information will be collected on the location of the patency, length of the patency (cm), diameter of the patency (mm), the presence of flow (Y/N), the presence of reflux (Y/N), and the presence of thrombus (Y/N). For subjects treated with surgical stripping, anatomic closure of the primary target vein is defined as the absence of clinically significant refluxing truncal vein incompetency and no discrete segments of patency exceeding 5 cm in the primary target vein. Any areas with vein remnants will be measured and information will be collected on the location of the remnant, length of the remnant (cm), the presence of flow (Y/N), the presence of reflux (Y/N), and the presence of thrombus (Y/N). Lack of anatomic closure on the date of the index procedure will not be considered relevant to this endpoint, since some treatments may not achieve closure immediately.

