7.9.1.2.4 Analysis Methods

For the return to work endpoint, a Kaplan-Meier survival estimator will be used to estimate the survival functions for both the VenaSeal™ and the control arm (i.e., ETA or Surgical Stripping). Day zero is the date of the index procedure. The censoring time is the time to study exit, the later of either the last contact date or the discontinuation date, or the time point for analysis, whichever comes first. A cumulative incidence figure will be produced to compare the two treatments. A log-rank test will be used to test whether the survival distributions differ between the treatment groups. If a patient is reported to have returned to work, but the date of return is unknown, the return date will be imputed from the date of the follow-up visit. For those who have returned to work, the median, Q1, Q3, minimum, and maximum will summarize the number of days to return to work, as well as the number who have not returned to work in each treatment arm.

The treatment effect for primary target vein closure at 6 months, one of the key secondary endpoints, is the difference in the survival curves at time t for each randomized study. A Kaplan-Meier survival estimator will be used to estimate each curve. Day zero is the date of the index procedure. The censoring time is the time to last study visit (scheduled or unscheduled), the time point for analysis, or time to exit, whichever comes first. The non-inferiority test for treatment (VenaSeal) versus control (ETA or Surgical Stripping) will be performed using the test statistic proposed in da Silva, Logan and Klein (2009)³. The Z test statistic will calculate $S_A(t) - S_C(t) + 0.10$ for the numerator where t is at 6 months and the square root of the sum of the Greenwood's variance estimators for each of $S_A(t)$ and $S_C(t)$ in the denominator.

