The rate of reintervention will be summarized by treatment arm in each study. The rate is calculated such that the numerator is the number of reinterventions and the denominator is the number of vein-years of follow-up. The amount of follow-up per person is defined as their date of exit or last known follow-up minus their date of index procedure. The vein-years is the amount of person-years times the number of target veins. A Poisson model will compare the rate of reintervention between treatment arms, using the number of reinterventions as the outcome and the person years of follow-up as an offset.

Determination of Subjects for Analysis

The reintervention analysis will consist of the ITT population.

5. Time to reintervention of any target vein (including primary target vein) through 60 months, as measured by the time between the index procedure and the first reintervention procedure. Subjects enrolled in the VenaSeal vs. Surgical Stripping Study will be followed through the 12 months visit only.

Hypothesis

The following hypothesis will be tested:

$H_0: S_A(t) = S_C(t)$

$H_a: S_A(t) \neq S_C(t)$

where $S_A(t)$ and $S_C(t)$ are the survival function estimates at time point t in the VenaSeal™ system arm and the ETA or surgical stripping arm, respectively. In the VenaSeal vs. Surgical Stripping Study, $t=12$ months and is otherwise $t=60$ months.

Endpoint Definition

A reintervention is a retreatment of any segment of any target vein in the target limb previously treated as part of the study at the index procedure.

Analysis Methods

The time to reintervention will be summarized by treatment arm in each study. Time to the first reintervention of any target vein by treatment will be presented with Kaplan-Meier estimation. Day zero is the date of the index procedure. The censoring time is the time to study exit, the later of either the last

contact date or the discontinuation date, or the time point for analysis, whichever comes first. A log-rank test will be used to compare arms.

Determination of Subjects for Analysis

The reintervention analysis will consist of the ITT population.

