The probability of experiencing an SAE through 12 months will be summarized by treatment arm in each study. The probability for each treatment arm will be estimated using the Kaplan-Meier method. Day zero is the date of the index procedure. The censoring time is the time to study exit, the later of either the last contact date or the discontinuation date, or the time point for analysis, whichever comes first. The DVT and PE events will be summarized by reporting the number of events of each type and the number of patients in which they occurred, by treatment arm. Additionally, summary statistics will report the proportion of SAEs. Numerator is the number of target limbs (or subjects) with an SAE through 12 months, denominator is the number of target limbs (or subjects).

Determination of Subjects for Analysis

The safety analysis will consist of the ITT population.

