7.9.2.3 Effectiveness secondary endpoints

The following ulcer-specific effectiveness endpoints will be evaluated:

1. Ulcer healing rate

Endpoint Definition

Ulcer healing rate is calculated by the percentage of the ulcer area healed, which is

$$100 * (1 - \text{Area}_k / \text{Area}_0)$$

for subject visit k . Area_0 indicates the wound area at baseline in cm^2 . Measurements are taken by an independent core laboratory through 24 months or until ulcer healing has been confirmed. When the ulcer healing is confirmed, the ulcer healing percentage shall be set to 100. If Area_k is larger than Area_0 , then the percentage is set to 0.

Analysis Methods

Mean, standard deviation and sample size will be presented on Ulcer healing rate. Summary statistics will also be provided for area at baseline and area at each subject visit k .

Determination of Subjects for Analysis

ITT population with data available will be used.

2. Ulcer recurrence on the target limb through 60 months.

Endpoint Definition

Sites document the occurrence of an ulcer recurrence at subject visits along with the date of the recurrence.

Analysis Methods

The Kaplan-Meier estimates through 60 months on the time to ulcer recurrence will be provided. The subjects who are lost to follow up or exit without recurrence will be censored at the time of last contact. Day 0 is the day of ulcer healing.

Determination of Subjects for Analysis

Subjects from the ITT population with healed ulcers

3. Ulcer-free time

Endpoint Definition

Days between initial ulcer healing and first ulcer recurrence, as applicable, through 60 months.

Analysis Methods

Summary statistics including mean, standard deviation, median, minimum and maximum will be provided.

Determination of Subjects for Analysis

Subjects who have experienced a healed ulcer followed by an ulcer recurrence.

The following generic effectiveness endpoints will be evaluated:

4. Anatomic closure of the primary target vein at 30 days, and 12, 24, 36, 48 and 60 months:

Endpoint Definition

For subjects treated with the VenaSeal™ system it is defined as DUS showing vein closure, for the primary target vein, along the entire treated vein segment with no discrete segments of patency exceeding 5 cm.

Analysis Methods

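### Several time-to-event endpoints censor at the later of last contact and discontinuation, so subjects lost to follow-up count as event-free while nobody is observing them

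*SAP*

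**What the plan says.** SAP 7.9.1.2.4 sets the rule for return to work, a formally tested key secondary endpoint: "The censoring time is the time to study exit, the later of either the last contact date or the discontinuation date", or the analysis time point if that is earlier. No analysis time point is named for this endpoint.

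The same rule appears in:
- SAP 7.9.1.4 item 5 (time to reintervention)
- SAP 7.9.1.5 (SAE curve): "the later of either the last contact date or the discontinuation date, or the time point for analysis, whichever comes first"
- SAP 7.9.1.7 (return to normal activities)
- SAP 7.9.2.4 and 7.9.2.6 (VLU Study: SAE, return to work, return to normal activities).

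Two further places point the same way. SAP 7.4 censors dropouts at discontinuation, and SAP 7.9.1.2.2 says of return to work: "Patients will be censored at the time of study exit".

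Other endpoints in the same SAP use different rules. Vein closure is censored at the earliest of last study visit, time point and exit. VLU ulcer healing is censored at the last follow-up visit. For ulcer recurrence, subjects "lost to follow up or exit without recurrence will be censored at the time of last contact". The rate endpoints end follow-up at exit or last known follow-up, without saying which applies when the two differ.

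Protocol 10.17.3 governs when a subject counts as lost: "A subject will not be considered lost to follow-up unless all efforts to obtain compliance are unsuccessful". The minimum is three telephone attempts, then a traceable letter, and the site should contact the study team before exiting the subject.

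**The concern.** Kaplan-Meier and log-rank methods treat a subject as at risk, and able to show an event, up to the censoring date. For someone lost to follow-up, nothing is normally known after the last contact. Moving the censoring date to a later administrative exit keeps that person in the risk set with no means of recording an event. The denominator is too large, and the cumulative event probability is biased downward.

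For return to work and return to activities, the event is the good outcome. Understating it means a lower apparent return and a longer apparent time off. For reintervention and SAEs, it means failure and harm look rarer than they are. If loss or the length of the gap differs between arms, the bias also enters the comparison. Return to work is the exposed case, because its log-rank test is part of the multiplicity procedure in SAP 7.5.

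**Working it through.** The plan gives no figure for this point, so there is nothing to reproduce. The check covers the gap that the rule creates, its effect on the estimates, and its effect on the test.

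**1. Length of the unobserved gap.** The documents do not say how the exit date is set for a lost subject. Assume exit is entered when the next missed visit window closes (Protocol Table 8):
- last seen day 30, next window closes day 210: 210 − 30 = 180 days
- last seen day 182, next window closes day 421: 421 − 182 = 239 days
- last seen day 365, next window closes day 786: 786 − 365 = 421 days, and the same for each later annual visit.

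The gap is thus about 6 to 14 months. On a curve capped at 12 months it is at most 365 − 182 = 183 days.

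**2. Reintervention to 60 months.** Assumed: event rate 5% per year, loss 5-10% per year, last contact at the last attended Table 8 visit, exit as in step 1, and no event seen after last contact. The true value is 1 − exp(−0.05 × 5) = 22.1%. By simulation:
- censored at last contact: about 22.1%
- SAP rule: about 21.1% at 5% loss and 20.2% at 10% loss.

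The relative understatement is (22.1 − 21.1)/22.1 = 4.5% to (22.1 − 20.2)/22.1 = 8.6%.

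**3. SAE to 12 months.** Same set-up with an assumed true probability of 10%:

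| Annual loss (assumed) | SAP rule | Relative to last-contact censoring |
|---|---|---|
| 5% | 9.7% | −2% |
| 10% | 9.6% | −5% |
| 15% | 9.4% | −7% |

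**4. Level of the return-to-work curve.** Two loss patterns, with *f* the fraction lost, *F* the true cumulative return and *S* = 1 − *F*. In both, the lost subject is exited after day 30.

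- *Lost before any answer.* Return by day 30 reads (1 − *f*) × *F*(30). With exponential times of mean 3 days, *F*(30) is essentially 100%. Losses of 2%, 5%, 7% and 10% then give 98%, 95%, 93% and 90%.
- *Lost after the day-7 answer.* Not returned at day 30 reads (1 − *f*) × *S*(30) + *f* × *S*(7). With a lognormal of median 4 days and sigma 1, *S*(7) is about 29% and *S*(30) about 2.2%. At *f* = 7% this gives 0.93 × 2.2% + 0.07 × 29% = 4.1%, against a true 2.2%. Under the plan's own ETA inputs (mean 3, SD 2, taken as normal), *S*(7) is only 2.3% and the effect is 0.07 × 2.3% = 0.16 points.

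**5. Log-rank test for return to work.** Equal true return times in both arms (lognormal as above), 66 workers per arm (assumed: half of 264/2 = 132), nominal two-sided 5%:

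| Loss pattern | Type I error, SAP rule |
|---|---|
| Equal loss, or unequal loss after the day-7 answer | 4-7% |
| 4% vs 10%, before any answer | about 16% |
| 3% vs 11%, before any answer | about 29% |

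Censoring at the last assessment holds the level at about 4-6%. Where the SAP rule inflates the error, the inflation grows with the number of workers per arm.

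**The case against.** The strongest reply is that the rule does little harm. Several parts of it stand.

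- **Equal loss.** Both return-to-work curves shift together and the test keeps its level. A reader might infer that the log-rank test is distorted in general, but the calculations do not support that. With loss after day 7, an extreme imbalance (0% vs 14%, 100 per arm) was needed to reach 12%.
- **Who is affected.** A withdrawal made at a contact leaves little or no gap. Protocol 10.17.4 allows safety contact for up to 30 days after exit in some cases, and there the later date is real observation. Healthcare use may be taken from medical records, and events are recorded from them, which would recover some SAEs and reinterventions.
- **Planned attrition.** A reader might take the 7% at 30 days in the sample-size section as the plan's own loss rate. It is an allowance for evaluable VenousTSQ scores. A missed day-30 questionnaire is not study exit, and Protocol 10.2 keeps later visits on schedule.
- **Length of the gap.** Lags of 12-18 months might be supposed, but Table 8 gives about 6-14 months under the stated assumption.
- **Later visits.** The 10.10 lists ask about return to work only at days 7 and 30, so a reader might infer that a subject not back by then is never asked again and stays a non-returner to 60 months. Protocol 10.5 says otherwise: "Return to work and return to normal activities will be assessed at follow-up visits until the subject has returned to each". Table 6 also marks patient-reported outcomes at every later visit. Time at risk after the last observed event changes neither the curve nor the test.
- **Different rules for different endpoints.** These are not wrong in themselves: closure and healing depend on imaging at visits.
- **Event-driven contact.** If an event itself prompts the contact, censoring at last contact can bias upward. The replacement rule should therefore rest on dates when status was assessed.

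None of this removes the bias for subjects who are lost to follow-up and whose exit date falls after the last assessment.

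**Conclusion.** The point holds for the estimates and, conditionally, for the return-to-work test. The censoring rule is explicit, and for lost subjects it counts unobserved time as event-free, which understates cumulative return, reintervention and SAE probabilities.

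Under the assumptions shown, the loss is about 1 to 2 percentage points on a 60-month reintervention probability of 22.1%, and about 2-7% in relative terms on the 12-month SAE probability. For return to work, the curve at day 30 falls by roughly the share lost before giving any answer, and by much less if loss comes after day 7 and most workers are already back.

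The test is at material risk only when loss differs between arms and mostly comes before the first answer. Unequal early loss is plausible in an open-label comparison of different procedures, but the documents give no loss rates by arm, so it is a possibility and not a prediction. The wording and direction are certain; the size is not. The change should be made before analysis.

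**What to change.** Replace the rule in SAP 7.9.1.2.4, 7.9.1.4 item 5, 7.9.1.5, 7.9.1.7, 7.9.2.4 and 7.9.2.6. Censor each endpoint at the last date on which its status was actually assessed, including any post-exit safety contact or record review, and cap this at a stated analysis time point. Name that time point for return to work and return to activities.

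In the same edit:
- Align SAP 7.4 and SAP 7.9.1.2.2, which would otherwise contradict the new rule.
- End person-time in the rate endpoints on the same date, in place of the present choice between exit and last known follow-up.
- Reconcile the Protocol 10.10 visit lists with 10.5 and Table 6, so that subjects not yet back are asked at the later visits.

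The cost is SAP wording plus a clarification of the visit lists, using existing visits. The downside is slightly less person-time and slightly higher event estimates.

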5.2 Duration

It is anticipated that enrollment will take approximately 36 months following enrollment of the first subject. The estimated study duration is approximately 8 years, including up to 60-month follow-up post-procedure and excluding the time required for preparing the final report. The expected duration of each subject's participation is up to 60 months after the index procedure, apart from subjects who were enrolled in the VenaSeal vs. Surgical Stripping Study. The latter will be followed through 12-months only.

Data will be recorded in the Case Report Form (CRF) at screening, baseline, index procedure (day 0), and during follow-up at 7 days (\pm 2 days), 30 days (\pm 7 days), 6 months (\pm 4 weeks), 12 months (\pm 8 weeks), 24 months (\pm 8 weeks), 36 months (\pm 8 weeks), 48 months (\pm 8 weeks) and 60 months (\pm 8 weeks).

Additional routine care visits can be conducted to accommodate adjunctive procedures 3 or more months following the index procedure (data for adjunctive procedures will be collected through 60 months), per the treating physician's discretion; these will not be considered study visits.

Data of subjects who were enrolled in the VenaSeal vs. Surgical Stripping Study will be recorded in the CRF at screening, baseline, index procedure (day 0), and during follow up at 7 days (\pm 2 days), 30 days (\pm 7 days), 6 months (\pm 4 weeks), and 12 months (\pm 8 weeks).

CEAP 6 subjects will have additional study visits until healing verification and data will be recorded in the CRFs at: 2 months (\pm 7 days), 3 months (\pm 7 days), 4 months (\pm 7 days), 5 months (\pm 7 days), 8 months (\pm 2 weeks), 10 months (\pm 2 weeks). If the healing has not occurred by 12 months, subjects will continue to follow standard wound care and remaining study visits. Subjects will come in for ulcer healing verification visits up to 24 months, after which no core laboratory ulcer assessment for wound healing will be required.

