Table 1: Return to work/normal activity time post treatment of venous reflux disease (External Data)

Author	Treatment type	Sample size (# pts, ITT)	Measure	Time in days to return to normal activities	Time in days to return to work
Pronk	ETA: Laser	62	Mean (SD)	3.2 (4.3)	4.4 (5.4)
Lurie	ETA: RFA	45	Mean (95% CI)	1.15 (0.05-2.34)	4.7 (1.16-8.17)
Gibson	VenaSeal™	50	Mean (SD)	2.4 (+/- 4.1)	0.2 (+/- 1.1)
Lurie	Surgical stripping	40	Mean (95% CI)	3.89 (2.67-5.12)	12.4 (8.66-16.23)
Pronk	Surgical stripping	68	Mean (SD)	3.2 (4.0)	4.2 (3.7)
Samuel	ETA: Laser	38	Median (IQR)	4 (1-14)	4 (0-12)
	ETA: Laser	38	Median (IQR)	3 (1-14)	3 (1-8)
Rasmussen	ETA: Laser	125	Median (range)	2 (0-25)	3.6 (0-46)
Cotton	ETA: Laser	212	Median		7.7
Lattimer	ETA: Laser	56	Median (IQR)	7.5 (2-15)	

Carradice	ETA: Laser	140	Median (IQR)	3 (1-10)	4 (2-14)
Rasmussen	ETA: RFA	125	Median (range)	1 (0-30)	2.9 0-14
Lane	ETA: RFA	83	Median (IQR)	2 (1-7)	2 (2-7)
Subramonia	ETA: RFA	48	Median (IQR)	3 (2-5)	10 (4-13)
Chan	VenaSeal™	29	Median (range)		1 (1-16)
Subramonia	Surgical stripping	45	Median (IQR)	12.5 (4-21)	18.5 (11-28)
Carradice	Surgical stripping	140	Median (IQR)	14 (7-25)	14 (13-28)
Cotton	Surgical stripping	294	Median		11.7
Rasmussen	Surgical stripping	125	Median (range)	4 (0-30)	4.3 (0-42)

The null hypothesis for the key secondary endpoint is that the VenaSeal™ system arm will have the same days to return to work as that of the control (ETA or surgical stripping) arm. The alternative hypothesis is that the VenaSeal™ system arm will have different days to return to work than that of the control arm. Rejection of the null hypothesis in favor of VenaSeal will signify that the ability to return to work after treatment with the VenaSeal™ system is superior to ETA or surgical stripping.

Specifically, the null (H_0) and alternative (H_a) hypotheses are:

$$H_0: r_A = r_C$$

$$H_a: r_A \neq r_C$$

Where r_A and r_C are the true days of return to work for the VenaSeal™ system arm and ETA or surgical stripping arm, respectively.

The parameter assumptions are:

- $r_A = 0.2$ in the VenaSeal™ system arm and $r_C = 3$ and 8 in ETA arm and surgical stripping arm, respectively
- standard deviation of 1.1 in the VenaSeal™ system arm, 2 in ETA arm and 3 in surgical stripping arm
- Two-sided t test with $\alpha = 0.0167$
- 1:1 randomization

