7.9.1.7 Patient Experience secondary endpoints

1. Time to return to normal activities as reported by the patients.

Hypothesis

For time to return to normal activities, the following hypothesis will be tested:

$$H_0: S_A(t) = S_C(t)$$

$$H_a: S_A(t) \neq S_C(t)$$

Where $S_A(t)$ and $S_C(t)$ are the survival functions for freedom from return to normal activities for the VenaSeal™ system arm and ETA or surgical stripping arm, respectively.

Endpoint Definition

Time to return to normal activities as reported by the patients.

Analysis Methods

For the return to normal activities endpoint, a Kaplan-Meier survival estimator will be used to estimate the survival functions for both the VenaSeal™ and the control arm (i.e., ETA or Surgical Stripping). A cumulative incidence figure will be produced to compare the two treatments. An event occurs when a patient indicates at a follow-up visit that they have returned to normal activities. The censoring time is the time to study exit, the later of either the last contact date or the discontinuation date, or the time point for analysis, whichever comes first. A log-rank test will be used to test whether the survival distributions differ between the treatment groups. If a patient is reported to have returned to normal activities, but the date of return is unknown, the return date will be imputed from the date of the follow-up visit. For those who have returned to normal activities, the median, Q1, Q3, minimum, and maximum will summarize the number of days to return to normal activities, as well as the number who have not returned to normal activities in each treatment arm.

Determination of Subjects for Analysis

The analysis will consist of the ITT population.

2. Intra-procedural and post-procedural pain at the index procedure, and 7 days and 30 days as reported by the patient using the numeric rating scale (NRS) with a scale of 0-10.

Hypothesis

There is no formal hypothesis test for this study objective.

Endpoint Definition

Pain is reported by the patient using a scale ranging from 0-10.

Analysis Methods

The total pain values at baseline, at each visit will be summarized within each treatment arm. In the VenaSeal vs. Surgical Stripping study, the pain information will further be summarized within types of anesthesia received during the procedure.

Determination of Subjects for Analysis

The analysis will consist of randomized subjects that underwent a procedure.

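### Dating an unknown return-to-work day to the follow-up visit dilutes the arm difference and, if unknown shares differ between arms, inflates the log-rank type I error, mainly in the VenaSeal vs ETA study

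*SAP*

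**What the plan says.** Return to work is one of two formally tested key secondary endpoints in each randomised study (SAP 7.5, 7.9.1.2). The analysis is Kaplan-Meier, and "A log-rank test will be used to test whether the survival distributions differ between the treatment groups" (SAP 7.9.1.2.4). The same section sets the date rule for a patient who has "returned to work, but the date of return is unknown, the return date will be imputed from the date of the follow-up visit". The same rule applies to return to normal activities: "but the date of return is unknown, the return date will be imputed from the date of the follow-up visit" (SAP 7.9.1.7 item 1). It also applies to both return endpoints in the single-arm VLU Study (SAP 7.9.2.6 items 1-2).

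On timing, Protocol 10.5 states: "Return to work and return to normal activities will be assessed at follow-up visits until the subject has returned to each". The Day 30 list in Protocol 10.10 carries the item "Ability to return to work/normal activities (only if not returned to work/normal activities by 7-day visit". Protocol Table 8 puts the Day 7 visit at day 5-9, the Day 30 visit at day 23-37 and the 6-month visit at day 154-210.

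The planning values in SAP 6.1.2 are 0.2 days "in the VenaSeal™ system arm and $r_C = 3$ and 8 in ETA arm and surgical stripping arm, respectively", with "standard deviation of 1.1 in the VenaSeal™ system arm, 2 in ETA arm and 3 in surgical stripping arm".

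**The concern.** If a patient has returned but the day is not known, the true day lies between the last visit at which the patient had not returned (day 0 if there was none) and the visit at which the return is reported. The rule always takes the right-hand end of that interval and treats it as observed. A VenaSeal patient who was back on day 1 becomes a day 5-9 event, or a day 23-37 event if the Day 7 question was missed. Until then the patient counts as not yet returned in every risk set.

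With planning means of 0.2 and 3 days, an imputed value of about 7 or 30 is late for either arm. Two consequences follow. If unknown dates are equally common in both arms, the difference is diluted. If they are not, the arm with more unknown dates looks slower even when the true distributions are the same.

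No other part of the SAP varies this rule. The day-of-week regression (6.1.2) and the AT and PP analyses (7.9.1.2.5) keep it. Multiple imputation (7.4, 7.9.1.1.6) covers the primary endpoints only. The date table in section 10 covers AE onset only. Nothing asks for the number of unknown return dates by arm, so a reader of the results could not judge the effect.

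**Working it through.** **1. The plan's own figure.** Unequal-variance t test, two-sided 0.0167, with power from the noncentral t:
- ETA: difference 3 − 0.2 = 2.8; SE = √((1.1² + 2²)/11) = 0.69; ratio 2.8/0.69 ≈ 4.1; power 90.1% at 11 per arm. The stated 22 subjects are reproduced.
- Stripping: difference 8 − 0.2 = 7.8; SE = √((1.1² + 3²)/5) = 1.43; ratio 7.8/1.43 ≈ 5.5; power 92.1% at 5 per arm. The stated 10 subjects are reproduced.

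These figures assume that every date is known. Log-rank power at 11 per arm with all dates known is also about 90%.

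**2. Numbers analysed.** The ETA study enrols about 264, or 132 per arm; the stripping study enrolled 108, or 54 per arm. Only employed patients count, and their share is not given. Assuming 60%: 0.6 × 132 ≈ 79 and 0.6 × 54 ≈ 32 per arm.

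**3. Simulation for the ETA study.** Assumptions: about 80 workers per arm, return times in whole days, unknown dates at random within arm and set to the reporting visit, two-sided log-rank at 0.05. The ranges allow for uncertainty in such assumptions as how many early returns are first reported at Day 30.

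| True means (days) | Unknown share | Rejection rate |
|---|---|---|
| 0.2 vs 3 (plan) | 10% both arms | about 97% or more |
| 0.2 vs 3 (plan) | 20% both arms | about 73-83% |
| 2 vs 3 | none | about 71% |
| 2 vs 3 | 5% both arms | 49-57% |
| 2 vs 3 | 10% both arms | 40-45% |
| 3 vs 3 (null) | equal shares | nominal |
| 3 vs 3 (null) | 5% vs 10% | about 9-10% |
| 3 vs 3 (null) | 5% vs 15% | 20-27% |

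**4. Sensitivity to the model.** With days drawn to match the planning means and SDs, 79 per arm and two-sided 0.0167:
- Plan effect: power is 99.5% at 10% unknown and 87% at 20% unknown in both arms, but 53% if 20% are unknown in VenaSeal and 5% in ETA.
- Null, both means 3: type I error is 1.7% at 20% in both arms, about 4% at 5% vs 10%, and 26-28% at 5% vs 20%.

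If every return by day 7 is reported at that visit (90 per arm, 0.05), power at the plan effect with 20% unknown is about 95%. False positives at a common mean of 3 are then about 10% (10% vs 5%) and 22% (15% vs 5%). The 73-83% in the table is therefore at the low end. The false-positive inflation appears under every set of assumptions.

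**5. Stripping study.** At the planning effect and 32 per arm, power is at least 99.9% in every case tried, up to 30% unknown in both arms. With both means at 8 days, type I error at nominal 1.67% is about 5-6% for 5% vs 20% unknown.

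**6. Does a different rule help?** With both means 3, 79 per arm and 5% vs 20% unknown, one draw from known same-arm times inside the interval cuts type I error from 26-27% to about 3%. The excess over 1.67% comes from using a single draw. Midpoint dating gives 2.0% there, but 37-40% when both means are 0.2 days, because the midpoint is still far too late.

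**The case against.** The strongest reply is that the test survives at the effect the plan expects. Return to work needs 22 evaluable subjects and the ETA study enrols about 264. Up to about 10% unknown in both arms costs almost nothing at 0.2 vs 3 days, and the stripping study is barely affected. This stands. A reader might infer that the endpoint is underpowered as planned, or that it is measured within a few days in both studies. The documents support neither: the stripping planning mean is 8 days, with literature values of 4.2 to 18.5 in SAP Table 1, and some ETA values there are 7.7 and 10.

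The second reply is that the bias needs both a material unknown share and an imbalance, and that recall at the Day 7 visit spans at most 9 days. This also stands. Open-label design and patient report mean that equal shares cannot be assumed, but they do not show which arm would have more unknown dates. A reader might infer a bias towards VenaSeal; nothing in the documents sets a direction.

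Third, the rule is pre-specified, and with equal shares it is conservative for a superiority claim. That is true, but pre-specification does not protect the type I error when shares differ.

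Fourth, SAP 7.9.1.2.4 summarises days by median, quartiles and range, and a median moves little with 10% late values. This is largely correct for the descriptive table, although SAP 7.9.1.2.3 also allows the mean to set the direction of a superiority claim.

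**Conclusion.** The point holds in conditional form. The rule places every unknown date at the end of its possible interval and calls it exact, and no stated analysis checks the effect. In the VenaSeal vs ETA study, equal unknown shares leave the type I error intact and dilute the difference. The dilution is negligible up to about 10% unknown at the planned effect, and substantial at about 20% or if the true difference is nearer one day. Unequal shares with no true difference raise a nominal 5% to about 9-10% (5% vs 10% unknown) or 20-27% (5% vs 15%), in favour of the arm with fewer unknown dates. The consequence for the stripping study is small.

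These sizes rest on assumed unknown-date rates, an assumed employed share of about 60%, and unknown dates occurring at random within arm. If almost no dates turn out to be unknown, the effect disappears. Larger false-positive rates can be produced with a shorter common mean or by dating many early returns to Day 30, but the documents do not support choosing those inputs.

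**What to change.** In SAP 7.9.1.2.4, 7.9.1.7 item 1 and 7.9.2.6 items 1-2:
- Treat a return with unknown date as lying between the last visit at which the patient had not returned (day 0 if none) and the reporting visit, and keep known dates exact.
- Analyse by multiple imputation within that interval, or by an interval-censored method, with an interval-censored log-rank for the randomised comparisons. Do not use single midpoint dating.
- Report the number of unknown dates by arm and by reporting visit.
- Keep visit-date imputation as a sensitivity analysis.

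No new data are needed. The cost is a SAP wording change, a little more programming and a less familiar test. The replacement still assumes that, within the interval, the fact that a date is unknown carries no information about the day of return; the SAP should say so.
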